 - Participants randomized in Phase 1 to the OMRON Connect App arm will complete the same survey questions as those in the Texting Arm. Participants using the OMRON connect app will also receive reminder messages on a similar frequency as the texting arm and will also be customized the participant's schedule as they can choose which days and times to receive push notification reminders delivered by the OMRON connect app. Upon receipt of the BP reading, participants will receive similar BP feedback (Appendix VII).
- Phase 2 (weeks 7-12):
 - At the conclusion of week 6, individuals will “crossover” to the opposite study arm and will continue in the study for an additional 6 weeks using the opposite technology to communicate their BP readings.

Motivating and positive affirmation messages will be sent to participants on a weekly basis (Appendix VII). After 4 weeks,

Study Protocol: Supporting Self-Management of Healthy Behaviors (SMART-HABITS)

and 8 weeks of the intervention, a usability survey (Appendix V) will be sent out to assess the ease of use of SMART-HABITS. Automated messages will be sent at key milestones to promote adherence to study procedures. Weekly feedback will be sent the morning after the end of the week. Daily feedback on performance from the prior day will be sent each morning.

Within SMART-HABITS' smartphone web-based application, there will be a portal which provides:

- Educational information that incorporates both clinical and lay-experiential CKD knowledge: Educational resources will present the health-related benefits of self-monitoring, reducing blood pressure, and increasing physical activity. Positive expectations will be outlined by ways that use self-monitoring BP and increasing physical activity may reduce the chances of experiencing negative health consequences.
- Graphical displays of personally set goals and real-time progress to goals
- Web links to social support

Throughout the study, if participants are identified to have low engagement with the intervention, identified through remote monitoring and defined as no BP readings for >1 week or no step counts in 4 days, they will undergo a re-engagement protocol. The re-engagement protocol includes the research team contacting participants with text messages to re-engage them and if after two attempts, the participant continues to not be engaged, they will be called and interviewed over the phone to provide more granular information to assess real-time barriers.

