
Additionally, this study will include the following data and safety monitoring plan.

Purpose: The data and safety-monitoring plan is written to ensure the safety of participants and verify the validity and integrity of the data. This monitoring plan details the source data verification of intervention, safety parameters, and the frequency of monitoring and regulatory document review.

Risk of Study: The study incurs minimal risk because the Way to Health research platform has proven to be safe in multiple prior behavioral health intervention studies, the technology and devices used in the feasibility trial are considered by the FDA to be general wellness products, and the real risk is to confidentiality.

Responsible Parties of Monitoring

1. Principal investigator: The PI will regularly monitor the data in collaboration with the research team.

Study Protocol: Supporting Self-Management of Healthy Behaviors (SMART-HABITS)

The PI will also be responsible for ensuring all source documentation exists for the data and all corrections are done according to the principles of Good Clinical Practice.

2. IRB: periodic review by the University of Pennsylvania's IRB.

3. Research Assistant (RA): during the course of the study, safety and data quality monitoring will be performed on an ongoing basis by the RA, in addition to the PI. The RA will be responsible for monitoring all data collected.

Ongoing Monitoring Meeting: monitoring days will be conducted periodically throughout the study; beginning no later than 2 weeks after the first participant is enrolled. Subsequent monitoring meetings will be every four weeks.

Assessing Adverse Events: Monitoring for adverse events will be conducted by the PI, [name], and the RA.

Participants will be asked an open-ended question via Way to Health to assess if participants are experiencing any medical concerns related to their participation in the study.

Reporting Events: Any side effects of notable medical concerns will be reported to the PI to determine a course of action.

Any adverse effect will be reviewed by [name] and [name] (primary mentor). After removal of identification information, all serious adverse events will be reported to the University of Pennsylvania IRB and the funding agency within 24 hours. All adverse events will be recorded and a summary table reviewed by the IRB annually.

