9.3 Confidentiality and Privacy

The risk of loss of confidentiality is paramount since we will have access to the participant's phone number but extensive efforts will be made to ensure that participants' confidentiality is maintained. To assure that participant confidentiality is preserved, individual identifiers (such as name) are stored in a single password protected system that is accessible only to research staff. Each participant will be assigned a unique study identification number and will never be tracked through the study by name, social security number, medical record number, and no other patient identifier other than mobile phone number. The study ID number will be used on all data collection instruments. A log of participant names, participant ID numbers, and pertinent registration information (e.g. emergency contact information) will be maintained in a locked area. Only de-identified data will be stored securely on servers.

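### The adverse-event question asks only about medical concerns related to participation, so the plan does not ensure the complete recording of adverse events it promises, and it does not ask about privacy harms

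*Combined protocol and SAP*

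**What the plan says.** The data and safety monitoring plan in section 8 (Safety Management) makes two commitments. On recording: "All adverse events will be recorded and a summary table reviewed by the IRB annually". On reporting, after de-identification: "all serious adverse events will be reported to the University of Pennsylvania IRB and the funding agency within 24 hours". Neither is restricted to events thought to be related to the study.

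The same section describes one way of soliciting events: "Participants will be asked an open-ended question via Way to Health to assess if participants are experiencing any medical concerns related to their participation". It gives no schedule and no look-back period for that question.

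On the nature of the risk, section 8 says that "the real risk is to confidentiality", and section 9.3 says: "The risk of loss of confidentiality is paramount since we will have access to the participant's phone number".

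Section 7.1 describes a re-engagement procedure for participants whose blood pressure or step data stop arriving. The team sends texts, and if two attempts fail, "they will be called and interviewed over the phone to provide more granular information to assess real-time barriers".

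**The concern.** The commitment covers all adverse events; the question covers a subset that the participant selects. Someone who has a dizzy spell, a fall on a walk or an admission, and who attributes it to kidney disease, can truthfully answer that there is nothing to report. Relatedness has then been settled by the participant, and no one on the study team has assessed the event.

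The question is also confined to medical concerns. The harm that the plan itself ranks first, loss of confidentiality, is not asked about. Some such harms may be known only to the participant, for example messages or readings seen by someone the participant did not choose.

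What is at stake is the meaning of the adverse-event table. If few events are listed, a reader cannot tell whether few occurred or few were asked about.

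**Working it through.** The documents give no adverse-event rate to reproduce, so the check is mainly a comparison of text.

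**Step 1. Commitment against question (both in section 8).**

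| | Commitment | Question as described |
|---|---|---|
| Relatedness | No limit | Only concerns related to participation |
| Kind of harm | All adverse events; confidentiality named as the real risk | Medical concerns only |
| Timing | Serious events reported within 24 hours | No frequency or look-back stated |

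The question is narrower on the first two rows and unspecified on the third.

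**Step 2. Does another described route close the gap?**

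| Route | What sets it off | Would it ask about a fall or admission the participant thinks unrelated? |
|---|---|---|
| Physician contact (7.1) | Very high transmitted blood pressure readings | Not unless such readings were sent |
| Re-engagement texts, then call (7.1) | Over a week without blood pressure data, or four days without step data | Stated purpose is barriers; no adverse-event question is given |
| Monitoring by the investigator and research assistant (8) | Ongoing, with meetings every four weeks | Reviews data collected; no further adverse-event source is named |
| Contact details on the dashboard (4.1) | Participant makes contact; described for withdrawal | Nothing is asked |
| Interview of those who choose not to continue (4.4) | Participant agrees | Purpose is feedback; no adverse-event question is given |
| Medical record (3.4.1, 5.1) | Screening blood pressure | No review for events during follow-up is described |

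Any of the first five may bring an event to light. None is described as asking for events whatever their cause, and none asks about privacy.

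**Step 3. What arithmetic can and cannot show.** The sample size is n = 40 (section 3.3.1). With zero recorded events, the exact one-sided 95% upper bound is 1 − 0.05^(1/n):

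- n = 40: 1 − 0.05^(1/40) = 0.072, or 7.2%.
- n = 32, if 20% are lost (40 × 0.8; 20% is the trigger in section 9.5 for enrolling more, not an expected rate): 1 − 0.05^(1/32) = 0.089, or 8.9%.

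Both bounds apply to the true risk only if every event is captured. The documents give neither the true 12-week risk p nor the share c of affected participants who are captured. To show direction only, take assumed values and compute the chance of an empty table, (1 − p·c)^40:

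| Assumed p | c = 1 | c = 0.5 | c = 0.25 |
|---|---|---|---|
| 5% | 0.129 | 0.363 | 0.605 |
| 10% | 0.015 | 0.129 | 0.363 |
| 20% | 0.000 | 0.015 | 0.129 |

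At an assumed 10% risk, an empty table would be rare with full capture (1.5%) but not with half capture (13%). Nothing in the documents supports one value of c over another, so this does not estimate an undercount.

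**The case against.** **The item itself has not been seen.** Section 8 states the purpose of an open-ended question; it does not give its wording. The surveys and message algorithm are in Appendices III to VII, which were not in the text reviewed. This stands as a limit: the finding concerns the protocol body, and the appendix items could be broader. The body would then still need to say so.

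**Other routes exist.** A reader might infer that the commitment to record all events cannot be met. The documents do not support that. The routes in the second table can surface events, and an interview about barriers could well turn up an illness or an admission. What can be said is that completeness is left to chance.

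**Disengaged participants.** A reader might also infer that the question is sent through a channel these participants no longer use. The text does not say so. Low engagement is defined by missing blood pressure or step data, which can come through the OMRON and Fitbit apps, not by unanswered Way to Health messages. Texts and a phone call follow. The gap is only that the call has no stated adverse-event question.

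**Privacy.** Sections 9.2 and 9.3 set out extensive safeguards, staff would find many breaches themselves, and the monitoring report already covers quality assurance and regulatory issues, where a breach can be placed. That is right, so no separate report line is needed. It does not help with a privacy problem that only the participant knows of.

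**Proportion.** Safety is not an endpoint in section 6. The minimal-risk statement rests on device classification and past use of the platform, and no rule for moving to a larger trial uses adverse-event counts. This limits the consequence. It does not remove the mismatch within section 8.

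**Conclusion.** The point holds for the protocol body. Section 8 promises unrestricted recording and reporting but describes a question restricted to related medical concerns, and no other described procedure makes up the difference. Privacy harms are not solicited although the plan ranks them first. Complete ascertainment is therefore not ensured, and a sparse adverse-event table would not be evidence of low risk.

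No size can be put on any undercount. A reader might be tempted to rescale the 7.2% bound by some capture rate, but any such rate would be invented. The feasibility endpoints in section 6.1 are not affected.

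The conclusion assumes that the question is asked as section 8 describes it and that the appendices add no broader one. It is worth correcting because the correction is cheap, not because the documents show that events will be missed.

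**What to change.** - Reword the question to be free of attribution: since the last contact, any new or worse health problem, fall, emergency visit or hospital stay, whatever its cause, and any privacy problem.
- Ask it in the existing week 4, week 8 and end-of-study surveys (sections 5.2, 7.1 and the informed consent section), and in the re-engagement phone call.
- State that the investigator, not the participant, assigns relatedness.
- Report how many participants answered at each time. The surveys run through Way to Health and will miss some people; the response count makes that visible, and the phone call offers a second route to those with low engagement.

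If the appendix items already ask this, amend section 8 to match them.

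The cost is about two survey items, an addition to the call script and a response count, with no new visits. The real downside is staff time: unrelated events will have to be logged, and unrelated serious ones, such as hospital stays, will come under the 24-hour reporting rule as section 8 now words it.

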9.1 Treatment Assignment Methods

All participants in the study will be assigned to the interventions but in a different order (first 6 weeks or second 6 weeks of the study) since this is a cross-over design.

9.2 Data Collection and Management

Questionnaires will be completed electronically through the Way to Health Platform on the SMART-HABITS app on a participant's smartphone or on a computer at enrollment (Appendix IV) and at the end of study (Appendix VI).

Questionnaires include:

1. Measure of CKD Knowledge: Kidney Knowledge Survey (KiKS)¹⁴⁷
2. Measure of e-health literacy: eHealth Literacy scale (eHEALS)- an eight-item measure of eHealth literacy developed to measure individuals' combined knowledge and perceived skills at finding, evaluating, and applying electronic health information to health problems.¹⁴⁸
3. Measure of chronic disease self-efficacy: Self-efficacy for Managing Chronic Disease Scale (SEMCDS)- 6 item scale.¹⁴⁹
4. Self-management in Chronic Disease: Partners in health scale^{150,151}
5. Kidney Disease Quality of Life (KDQOL-36)¹⁵², consists of five subscales:
 - o 1- Physical component summary (12 items about general health, activity limits, ability to accomplish desired tasks)
 - o 2 -Mental component summary (12 items depression and anxiety, energy level, and social activities)
 - o 3- Burden of kidney disease (4 items on how much kidney disease interferes with daily life, takes up time, causes frustration, or makes the respondent feel like a burden)
 - o 4- Symptoms and problems (12 items about how much respondent bothered by CKD related symptoms)
 - o 5- Effects of Kidney Disease on Daily life (7 items about much how respondent bothered by fluid limits, diet restrictions, ability to work around the house or travel, feeling dependent on doctors or other medical staff, stress or worries, sex life and personal appearance).

Several questions from the Attitudes toward mHealth and remote monitoring (10 item questionnaire).⁶⁹

Data collected from participants' smartphone using Fitbit app and OMRON Connect ap, including survey and questionnaire responses and will be sent electronically to the Way to Health research platform and stored on a secure data server. This system is hosted onsite at the University of Pennsylvania with a level of security identical to that used for the clinical data of patients within the University of Pennsylvania Health System.

Study Protocol: Supporting Self-Management of Healthy Behaviors (SMART-HABITS)

We will use Federal Information Processing Standards (FIPS) to assure secure, HIPAA-compliant data control and management to minimize risks by using rigorous data security protocols to protect subject confidentiality and comply with all federal and HIPAA requirements. Databases will be password protected, further restricting access to only study personnel. Interview transcript data will be labeled with a unique ID number, which will be linked in a separate password protected file, to demographic data. Study information will not be included in any medical records.

All study computers will sit behind the University's firewall protection and in locked offices. Further, our computers are continually scanned for vulnerability and to insure that no personal identifying information is found in appropriate places. All analyses will be conducted on de-identified data on secure computers. Lastly, using network firewall technologies, the database administrator will prevent the three major sources of data security problems: unauthorized internal access to data, external access to data, and malicious intent to destroy data and systems. Controlled user access will ensure that only appropriate and authorized personnel are able to view, access, and modify study data.

9.3 Confidentiality and Privacy

The risk of loss of confidentiality is paramount since we will have access to the participant's phone number but extensive efforts will be made to ensure that participants' confidentiality is maintained. To assure that participant confidentiality is preserved, individual identifiers (such as name) are stored in a single password protected system that is accessible only to research staff. Each participant will be assigned a unique study identification number and will never be tracked through the study by name, social security number, medical record number, and no other patient identifier other than mobile phone number. The study ID number will be used on all data collection instruments. A log of participant names, participant ID numbers, and pertinent registration information (e.g. emergency contact information) will be maintained in a locked area. Only de-identified data will be stored securely on servers.

All study staff will be reminded to appreciate the confidential nature of the data collected and contained in these databases. The Penn Medicine Academic Computing Services (PMACS) will be the hub for the hardware and database infrastructure that will support the project and is where the Way to Health web portal is based. The PMACS is a joint effort of the University of Pennsylvania's Abramson Cancer Center, the Cardiovascular Institute, the Department of Pathology, and the Leonard Davis Institute. The PMACS provides a secure computing environment for a large volume of highly sensitive data, including clinical, genetic, socioeconomic, and financial information. Among the IT projects currently managed by PMACS are: (1) the capture and organization of complex, longitudinal clinical data via web and clinical applications portals from cancer patients enrolled in clinical trials; (2) the integration of genetic array databases and clinical data obtained from patients with cardiovascular disease; (3) computational biology and cytometry database management and analyses; (4) economic and health policy research using Medicare claims from over 40 million Medicare beneficiaries. PMACS requires all users of data or applications on PMACS servers to complete a PMACS-hosted cybersecurity awareness course annually, which stresses federal data security policies under data use agreements with the university. The curriculum includes Health Insurance Portability and Accountability Act (HIPAA) training and covers secure data transfer, passwords, computer security habits and knowledge of what constitutes misuse or inappropriate use of the server. We will implement multiple, redundant protective measures to guarantee the privacy and security of the participant data. All investigators and research staff with direct access to the identifiable data will be required to undergo annual responsible conduct of research, cybersecurity, and HIPAA certification in accordance with University of Pennsylvania regulations. All data for this project will be stored on the secure/firewalled servers of the PMACS Data Center, in data files that will be protected by multiple password layers. These data servers are maintained in a guarded facility behind several locked doors, with very limited physical access rights. They are also cyber-protected by extensive firewalls and multiple layers of communication encryption. Electronic access rights are carefully controlled by University of Pennsylvania system managers. We believe this multi-layer system of data security, identical to the system protecting the University of Pennsylvania Health Systems medical records, greatly minimizes the risk of loss of privacy. In addition, risk of loss of confidentiality will be minimized by storing signed informed consent forms in locked file cabinets in locked offices accessible only to trained study staff. Each subject will be assigned a unique identifier without identifying information, and data will be entered into an electronic database using only the unique identifier. Only trained study staff will have access to the code that links the unique identifier to the subject's identity. Electronic data will be stored on secure, password-protected firewalled servers at the University of Pennsylvania.

The study team will work to uphold the privacy of the participants in several ways. First, any communications made among study staff regarding participants will use ID numbers only and never include names or other personal information. Second, all paper copies of participant data will be kept in locked files. Third, in all data sets, we will use ID numbers only.

Study Protocol: Supporting Self-Management of Healthy Behaviors (SMART-HABITS)

A separate list of linking names with ID numbers will be accessible by the research team that is kept separate from data collected for the pilot study in a password-protected file on a password protected computer in a locked office. Whether in person or by phone, the research team will ensure that no persons who are not authorized by study participants to share personal health information are in the room when discussing informed consent (Appendix I) or during data collection at the initial study visit or at the end of study interviews.

[name] and a research assistant will conduct the end-of-study interviews and will have formal training by the Mixed Methods Research Laboratory at the University of Pennsylvania. The training will include proper methods for handling sensitive issues that arise during the interviews (note that the interviews themselves are not intended to include sensitive issues but because of their open-ended nature this possibility must be considered). Data from the interviews will be transcribed using a HIPAA-compliant service and verbatim transcriptions will be provided to the study team void of any personal identifiers and thus, only anonymous data will be used for all analyses.

